2 ABBREVIATIONS

AE	- Adverse Event
ALT	- Alanine Aminotransferase
APAP	- n-acetyl-p-aminophenol (acetaminophen)
AST	- Aspartate Aminotransferase
AUC	- Area Under the Curve
BMI	- Body Mass Index
BUN	- Blood Urea Nitrogen
CFR	- Code of Federal Regulation
CK18	- Cytokeratin 18
CO ₂	- Carbon dioxide
CoA	- Coenzyme A
CRF	- Case Report Form
CRP	- C-Reactive Protein
CT	- Computed Tomography
CTCAE	- Common Terminology Criteria for Adverse Events
EC	- Ethics Committee
eCRF	- Electronic Case Report Form
EDC	- Electronic Data Capture
EU	- European Union
FDA	- Food and Drug Administration
GCP	- Good Clinical Practice
GI	- Gastrointestinal
GGTP	- Gamma-Glutamyl Transpeptidase
GRAS	- Generally Recognized As Safe

Exalenz Bioscience Ltd.	Last update on: May1, 2016
Study Title: Clinical Study of the BreathID [®] System to train the algorithm for the ¹³ C-Octanoate Breath Test with or without the ¹³ C-Methacetin Breath Test (OBT and MBT respectively) for correlation with histological findings of Non-Alcoholic Fatty Liver Disease (NAFLD)	Protocol No.: NASH-EX-1114
	Version: 1f
Document N^o: CSD00080	Page 7 of 61

HbA1c	- Hemoglobin A1c
HCC	- Hepatocellular Carcinoma
HCO ₃	- Bicarbonate
HCV	- Hepatitis C Virus
HE	- Hepatic Encephalopathy
HVPG	- Hepatic Venous Pressure Gradient
IC	- Informed Consent
ICF	- Informed Consent Form
ICH	- International Conference of Harmonization
IDE	- Investigational Device Exemption
IL6	- Interleukin 6
INR	- International Normalized Ratio (for prothrombin time)
IRB	- Institutional Review Board
K ⁺	- Potassium
MBT	- ¹³ C-Methacetin Breath Test
MCS	- Molecular Correlation Spectrometry
MELD	- Model for End-stage Liver Disease
MRI	- Magnetic Resonance Imaging
Na ⁺	- Sodium
NAFLD	- Non-Alcoholic Fatty Liver Disease
NAS	- NASH Activity Score
NASH	- Non-Alcoholic Steato-Hepatitis
NASH CRN	- NIH NASH Clinical Research Network
NIH	- National Institute of Health
NPV	- Negative Predictive Value
NSBB	- Non-Selective Beta Blocker

Exalenz Bioscience Ltd.	Last update on: May1, 2016
Study Title: Clinical Study of the BreathID [®] System to train the algorithm for the ¹³ C-Octanoate Breath Test with or without the ¹³ C-Methacetin Breath Test (OBT and MBT respectively) for correlation with histological findings of Non-Alcoholic Fatty Liver Disease (NAFLD)	Protocol No.: NASH-EX-1114
	Version: 1f
Document N^o: CSD00080	Page 8 of 61

OUS	- Out of the United States
O ₂	- Oxygen
OBT	- ¹³ C-Octanoate Breath Test
PHT	- Portal Hypertension
PPV	- Positive Predictive Value
PT	- Prothrombin Time
PTT	- Partial Thromboplastin Time
ROC	- Receiver Operating Characteristic
SAE	- Serious Adverse Event
SUSAR	- Suspected Unexpected Serious Adverse Reactions
TNF α	- Tumor Necrosis Factor Alpha
TIPS	- Transjugular Intrahepatic Portosystemic Shunt
US	- United States (of America)
US	- Ultrasound
USA	- United States of America
WBC	- White Blood Cells

Exalenz Bioscience Ltd.	Last update on: May1, 2016
Study Title: Clinical Study of the BreathID [®] System to train the algorithm for the ¹³ C-Octanoate Breath Test with or without the ¹³ C-Methacetin Breath Test (OBT and MBT respectively) for correlation with histological findings of Non-Alcoholic Fatty Liver Disease (NAFLD)	Protocol No.: NASH-EX-1114
	Version: 1f
Document N^o: CSD00080	Page 9 of 61

3 PROTOCOL SYNOPSIS

Protocol Title:	Clinical Study of the BreathID [®] System to train the algorithm for the ¹³ C-Octanoate Breath Test with or without the ¹³ C-Methacetin Breath Test (OBT and MBT respectively) for correlation with histological findings of Non-Alcoholic Fatty Liver Disease (NAFLD)
Protocol Number:	NASH-EX-1114
Version and Date:	v 1f, May1, 2016
Investigational subject:	Biopsy characteristics of patients suspected of Non-Alcoholic Fatty Liver Disease (NAFLD)
Investigational Product	BreathID [®] System together with ¹³ C-labeled Octanoate and ¹³ C-labeled Methacetin
Primary Objective:	The primary objective of the study is to develop an algorithm based on OBT with or without MBT with or without additional clinical and/or laboratory parameters, and its cut-off to correlate with histological findings of NAFLD.
Primary Endpoint:	Correlation of histological findings, as assessed by a central reader, of NAFLD compared to ¹³ C-Octanoate Breath Test with or without ¹³ C-Methactin Breath Test with or without additional clinical and/or laboratory parameters
Secondary Endpoint:	Correlation between OBT±MBT and clinical course (i.e. clinical outcome: liver decompensation events etc.) at 18 and 36 months post the last breath test performed (visit / phone). NOTE: Patients undergoing intervention for NASH / NAFLD, including both approved and experimental approaches prior to the defined time points will be terminated hence will not be evaluated for this endpoint.
Safety Endpoints:	Safety will be assessed by reviewing all adverse and serious adverse events occurring in all subjects enrolled from the time of enrollment until the subject completes the protocol.

Exalenz Bioscience Ltd.	Last update on: May1, 2016
Study Title: Clinical Study of the BreathID [®] System to train the algorithm for the ¹³ C-Octanoate Breath Test with or without the ¹³ C-Methacetin Breath Test (OBT and MBT respectively) for correlation with histological findings of Non-Alcoholic Fatty Liver Disease (NAFLD)	Protocol No.: NASH-EX-1114
	Version: 1f
Document N^o: CSD00080	Page 10 of 61

Any AEs reported that are possibly or probably related to the use of the product or related to the procedure within 36 months post last breath test performed or until subject termination will be followed until resolution and if laboratory work is done secondary to AEs and found abnormal, these tests will be followed until normalization or stabilization.

Study Design:

A multicenter, non-randomized, open label, cross-sectional comparative exploratory study comparing OBT with or without MBT values to histology.

This study will be used to train an algorithm using OBT with or without MBT with or without clinical and/or laboratory parameters correlating with histological findings of NAFLD.

Study Population:

At least 200 consecutive patients suspected of having NAFLD with a fresh liver biopsy (within 6 months before or 1 month after) indicated to rule-out / confirm NAFLD, meeting all inclusion/exclusion criteria will be enrolled.

Inclusion Criteria:

1. Adult men or women (≥ 18 years of age)
2. Liver biopsy performed indicating NAFLD/NASH performed within 6 months prior to both breath-tests
NOTE: The samples must meet pre-defined quality criteria. (See Appendix II for biopsy quality requirements)
OR:
Undergoing Liver biopsy to rule-out or confirm NAFLD/NASH.
3. No other known co-existent liver disease, excluded by appropriate serologic / other testing
4. Patient able and willing to sign an Informed Consent Form
5. Can tolerate an overnight (8-hour) fast

Exclusion Criteria:

1. Positive studies for any of the following within three years prior to biopsy
 - a. Anti HCV positive
 - b. HBsAg positive

Exalenz Bioscience Ltd.	Last update on: May1, 2016
Study Title: Clinical Study of the BreathID [®] System to train the algorithm for the ¹³ C-Octanoate Breath Test with or without the ¹³ C-Methacetin Breath Test (OBT and MBT respectively) for correlation with histological findings of Non-Alcoholic Fatty Liver Disease (NAFLD)	Protocol No.: NASH-EX-1114
	Version: 1f
Document N^o: CSD00080	Page 11 of 61

- c. Iron saturation > 60% + gene test for hereditary hemochromatosis or iron overload as defined by presence of 3+ or 4+ stainable iron on liver biopsy
 - d. Antinuclear antibody at a titer > 1: 160 along with hypergammaglobulinemia and 5 times ALT normal levels
 - e. Alpha-1-antitrypsin level below lower limit of normal (< 150 mg/dl) or no PAS diastase resistant globules on biopsy.
 - f. Primary biliary cirrhosis as defined by elevation of alkaline phosphatase greater than upper limit of normal and anti-mitochondrial antibody (AMA) of greater than 1:80 and consistent liver histology
 - g. Low level of ceruloplasmin (< 10 ng/mL)
 - h. Drug-induced liver disease as defined on the basis of typical exposure and history
Note: These studies do not need to be performed if they are not available, as it is assumed that if they are not on file, the condition does not exist
2. Patients known to have chronic liver disease other than NAFLD as routinely diagnosed by the investigator
 3. Concurrent acute hepatic condition other than NAFLD
 4. Alcohol consumption > 20 gm/day (0.71 oz./day) for women and > 30 gm/day (1.06 oz./day) for men
 5. Drugs that may interfere with octanoate metabolism or can also cause NAFLD independent of the metabolic syndrome, including: corticosteroids, amiodarone, tetracycline, valproic acid, methotrexate, stavudine, zidovudine
 6. When MBT is performed subject should not have taken any of the following at least 48 hours prior to the breath test: Acyclovir, allopurinol, carbamazepine, cimetidine, ciprofloxacin, daidzein, (herbal) disulfiram, echinacea, enoxacin, famotidine, fluvoxamine, methoxsalen, mexiletine, montelukast, norfloxacin, phenylpropanolamine, phenytoin, propafenone, rifampin, terbinafine, ticlopidine, thiabendazole, verapamil, zileuton or any medication that might interfere with Methacetin metabolism or might affect CYP 1A2
 7. Patients that have had more than 10% weight change between biopsy and enrollment.

Exalenz Bioscience Ltd.	Last update on: May1, 2016
Study Title: Clinical Study of the BreathID [®] System to train the algorithm for the ¹³ C-Octanoate Breath Test with or without the ¹³ C-Methacetin Breath Test (OBT and MBT respectively) for correlation with histological findings of Non-Alcoholic Fatty Liver Disease (NAFLD)	Protocol No.: NASH-EX-1114
	Version: 1f
Document N^o: CSD00080	Page 12 of 61

8. Hypersensitivity to any of the study substrates: Octanoate or Methacetin and their metabolites, i.e. paracetamol, acetaminophen.
9. Known extra-hepatic diseases including but not limited to: severe congestive heart failure (NIHA>2), known severe pulmonary hypertension (>35 mmHg), history of chronic obstructive pulmonary disease or uncontrolled symptomatic bronchial asthma or uncontrolled diabetes mellitus (HA1c>9.5%)
10. Previous surgical GI bypass surgery
11. Extensive small bowel resection (>100 cm)
12. Known uncontrolled malabsorption or diarrhea
13. Concurrent total parenteral nutrition
14. Any organ transplant
15. Patients receiving any anti-viral treatment or any other liver directed therapy, procedure or surgery between the time of the biopsy and the breath test
16. Pregnant or breast feeding
17. Patients unable or refusing to sign informed consent
18. Patients that, based on the opinion of the investigator, should not be enrolled into this study due to safety / adherence reasons.
19. Patients participating in other clinical trials and already receiving experimental treatments or procedures
20. Patients with suspected or documented hepatocellular carcinoma by ultra-sound or other imaging modality
21. Patients diagnosed with partial / complete portal venous occlusion, hepatic venous occlusion, previous PHT surgery, or placement of a transjugular intrahepatic portosystemic shunt (TIPS) according to initial imaging studies.

On the day of the OBT/MBT:

1. 8 hours fasting prior to OBT/MBT including all PO morning medications except for beta blockers. Diabetic patients that are driving should test their blood sugars to rule out hypoglycemia and respond accordingly.
2. No Smoking on the day of the MBT
3. No paracetamol (acetaminophen) based medications within 24 hours prior to MBT

Exalenz Bioscience Ltd.	Last update on: May1, 2016
Study Title: Clinical Study of the BreathID [®] System to train the algorithm for the ¹³ C-Octanoate Breath Test with or without the ¹³ C-Methacetin Breath Test (OBT and MBT respectively) for correlation with histological findings of Non-Alcoholic Fatty Liver Disease (NAFLD)	Protocol No.: NASH-EX-1114
	Version: 1f
Document N^o: CSD00080	Page 13 of 61

4. No general anesthesia or sedation within 24 hours prior to OBT/MBT
5. No alcohol within 24 hours prior to OBT/MBT
6. Patient should be symptom free of any prior intervention (e.g. biopsy)

Listing of Study Procedures:

1. Informed consenting and eligibility including fresh liver biopsy confirmed to meet quality standards (see Appendix II)
2. Baseline and Physical Examination
3. Blood drawing for:
 - a. Insulin and Glucose
 - b. Complete Blood count (WBC, Hemoglobin, Platelets) and CRP
 - c. Coagulation: PT (INR)
 - d. Renal panel and electrolyte panel (BUN, creatinine, electrolytes (Na⁺ and K⁺),
 - e. Collection of 4ml of blood for serum and freezing for storage (no preservative tube) where possible.
 - f. Hepatic panel (AST, ALT, alkaline phosphatase, GGTP, total bilirubin, direct bilirubin, serum albumin and total protein) - if not available from within 3 months
 - g. Additional Coagulation Panel (PTT, fibrinogen) - if not available from within 3 months
 - h. Total calcium, PO₄ (phosphate corrected), magnesium - if not available from within 6 months
 - i. Lipid profile and HbA1c - if not available within 6 months
 - j. Thyroid Panel - if not available within 12 months
 - k. Other assays where routinely practiced; (optional): Adiponectin + Leptin + IL6 + CK18, TNF α , C-peptide
4. OBT - ¹³C-Octanoate Breath Test (within 6 months of liver biopsy or within 1 month before liver biopsy) and ensuring MBT is feasible within 30 days but not less than 48 hours). If done on same day, OBT must be performed before the biopsy.
5. MBT - ¹³C-Methacetin Breath Test (within 30 days post OBT but not less than 48 hours). If done on the same day as the liver biopsy, the MBT must be performed before the biopsy.
6. Safety monitoring phone call 48 hours post last breath test. Any AEs reported that are possibly or probably related to the use of the product or related to the

Exalenz Bioscience Ltd.	Last update on: May1, 2016
Study Title: Clinical Study of the BreathID [®] System to train the algorithm for the ¹³ C-Octanoate Breath Test with or without the ¹³ C-Methacetin Breath Test (OBT and MBT respectively) for correlation with histological findings of Non-Alcoholic Fatty Liver Disease (NAFLD)	Protocol No.: NASH-EX-1114
	Version: 1f
Document N^o: CSD00080	Page 14 of 61

procedure will be followed until resolution and if laboratory work is done secondary to AEs and found abnormal, these tests will be followed until normalization or stabilization.

7. Follow-up Visit 18 months post last breath test performed: clinical evaluation (in person or telephone)
8. Follow-up Visit 36 months post last breath test performed: clinical evaluation (in person or telephone)
9. Any AEs reported that are possibly or probably related to the use of the product or related to the procedure within 36 months post last breath test performed or until subject termination will be followed until resolution and if laboratory work is done secondary to AEs and found abnormal, these tests will be followed until normalization or stabilization.

Rules of discontinuations (Subject and/or Study):

1. Withdrawal of patients from the study if they have a CTCAE (Common Terminology Criteria for Adverse Events) Grade 3 or higher regardless of whether the event is attributed to the drug unless it is caused by an accident that could not reasonably be attributable to the drug (CTCAE: Common Terminology Criteria for Adverse Events Version 4.0)
2. Discontinuance of study, if ≥ 2 patients on Octanoate/Methacetin develop the same CTCAE Grade 3 event or 1 patient develops a CTCAE Grade 4 or higher event due to one of the breath tests

[figure not shown]
Data Analysis / Statistics: An ROC analysis will be used to determine the optimal parameter and cut-offs for required performance measures sensitivity and specificity.

All efficacy analysis will include the point estimates of sensitivity, specificity, PPV and NPV with respective exact 95% confidence intervals. The respective Positive and Negative Predictive Values (PPV and NPV) will be presented as a function of possible NAFLD prevalence and will include the prevalence of the enrolled population.

This test will not replace biopsies to rule out other liver diseases such as autoimmune hepatitis, alcoholic hepatitis, alpha-1-antitrypsin deficiency, etc.

Exalenz Bioscience Ltd.	Last update on: May1, 2016
Study Title: Clinical Study of the BreathID [®] System to train the algorithm for the ¹³ C-Octanoate Breath Test with or without the ¹³ C-Methacetin Breath Test (OBT and MBT respectively) for correlation with histological findings of Non-Alcoholic Fatty Liver Disease (NAFLD)	Protocol No.: NASH-EX-1114
	Version: 1f
Document N^o: CSD00080	Page 15 of 61

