5.1.2 The importance of diagnosing and characterizing NASH

The public health priority of any disease is based on three considerations: (1) prevalence, (2) impact of disease on the affected individuals and (3) availability of effective therapy.

Since the gold-standard for diagnosis of NASH and other liver diseases is a liver biopsy, hospital-based studies with liver biopsies are subject to ascertainment bias. Population based studies have utilized imaging modalities such as ultrasound and MRI to diagnose NAFLD but are limited by the absence of histologic confirmation. Recently, specific changes on MRI have been correlated with hepatic lipid content and presence of NAFLD may be diagnosed with relative confidence. Based on MRI, it has been estimated that the overall prevalence of NAFLD in the United States is about 30%⁽³⁾. MRI does not distinguish between NAFL and NASH⁽⁴⁾. Approximately

Exalenz Bioscience Ltd.	Last update on: May1, 2016
Study Title: Clinical Study of the BreathID [®] System to train the algorithm for the ¹³ C-Octanoate Breath Test with or without the ¹³ C-Methacetin Breath Test (OBT and MBT respectively) for correlation with histological findings of Non-Alcoholic Fatty Liver Disease (NAFLD)	Protocol No.: NASH-EX-1114
	Version: 1f
Document N^o: CSD00080	Page 18 of 61

4-5% of the US population is estimated to have NASH. NAFL is associated with a benign clinical course and the majority of cases of NAFL remain asymptomatic and free of fibrosis or development of steatohepatitis over a 5-10 year time frame from diagnosis⁽⁵⁾. On the other hand, NASH can progress to cirrhosis in about 20% of the cases⁽⁶⁾.

About 15% of cases referred for liver transplant have either NASH or cryptogenic cirrhosis, which is believed to be the end result of NASH⁽⁷⁾.

5.1.3 Defining the need for a non-invasive test for the diagnosis and characterization of NASH and other liver conditions

About 7.9% of the US population has persistently elevated liver enzymes with negative findings for viral hepatitis and other common causes of liver diseases⁽⁸⁾. Over 80% of such cases are estimated to be due to NAFLD (NAFL or NASH). In those who have concomitant features of the metabolic syndrome, the likelihood of NAFLD exceeds 90%. However, there are no noninvasive ways to distinguish between NAFL and NASH. Moreover, NASH would progress to cirrhosis in approximately 20% of the cases⁽⁶⁾ hence requires disease surveillance..

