11.7.5 Performance Analysis

A model/algorithm will be developed for the correlation between histological findings of NAFLD and OBT with or without MBT. It will be developed using either logistic regression or neural network or any other known methodology. Using a cut-point on the score a binary diagnosis of NASH (Yes/No) or NAFL (Yes/No) will be obtained. The minimal criterion for sufficient efficacy is an Area under the Receiver Operating Characteristics (ROC) Curve (AUC) ≥ 0.75 in this patient population. A potential clinical utility was designated for the algorithm/model output; where this algorithm could aid the clinician in ruling-in or out NASH or NAFL. This will be translated into finding a model prediction cut-point that provides a high sensitivity (true positive rate) and at least moderate specificity (true negative rate), which in turn achieves a high negative predictive value (NPV). High NPV is considered to be near 90% (i.e. 88%) thus sensitivity should be at least 90% and specificity should be at least 50%. Cross validation methods will be used to test algorithm stability.

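### PPV and NPV are indexed by NAFLD prevalence, but the cut-point diagnoses NASH or NAFL, and each of these has its own prevalence

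*Combined protocol and SAP*

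**What the plan says.** The Data Analysis / Statistics part of the synopsis (section 3) has two sentences on this. The first reads: "All efficacy analysis will include the point estimates of sensitivity, specificity, PPV and NPV with respective exact 95% confidence intervals". The second says that PPV and NPV "will be presented as a function of possible NAFLD prevalence and will include the prevalence of the enrolled population". It gives no range of prevalences and no interval method.

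Section 11.7.5 fixes what the test classifies: "Using a cut-point on the score a binary diagnosis of NASH (Yes/No) or NAFL (Yes/No) will be obtained". It aims for sensitivity of at least 90%, specificity of at least 50% and an NPV of about 88 to 90%, without stating a prevalence. Neither section 11.7.5 nor the rest of section 11 repeats the prevalence display.

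Section 5.1.3 treats NAFLD as NAFL or NASH. Section 5.1.2 puts US prevalence at about 30% for NAFLD and says "4-5% of the US population is estimated to have NASH". Section 11.5 plans 200 subjects, with at least 50 positive for NASH and at least 50 positive for what it calls NAFLD.

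**The concern.** PPV and NPV are governed by the prevalence of the condition that the test calls present or absent. That condition is NASH in one use of the cut-point and NAFL in the other. NAFLD is their union, so where both are present its prevalence exceeds that of either.

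NPV falls and PPV rises as prevalence rises. Reading a NASH test at NAFLD prevalence therefore understates NPV and overstates PPV. The stated use is rule-out by a high NPV, so the reported figure could miss its target, or a cut-off could be judged unsuitable, because of the axis and not because of the test.

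The problem is sharpest at the one point that the plan commits to showing, the enrolled prevalence. One entry route (section 10.1, criterion 2) requires a biopsy already indicating NAFLD/NASH, so enrolled NAFLD prevalence will be high by design.

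**Working it through.** **Inputs.** Sensitivity (se) 0.90 and specificity (sp) 0.50, the targets in section 11.7.5. Prevalences come from sections 5.1.2 and 11.5, plus one assumed value, 80%, for NAFLD among enrolled patients. The documents do not give that figure. Section 5.1.3 puts NAFLD at over 80% of persons with persistently raised liver enzymes and no other common cause, which makes 80% plausible.

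**Formulas.** With prevalence p:
- NPV = sp(1−p) / [sp(1−p) + (1−se)p]
- PPV = se·p / [se·p + (1−sp)(1−p)]

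**The plan's own figure first.** Solving for p at NPV 0.88 gives p = 0.5×0.12 / (0.5×0.12 + 0.88×0.1) = 0.060/0.148 = 40.5%. For NPV 0.90 it is 0.050/0.140 = 35.7%. The documents state neither prevalence, so the 88% cannot be reproduced from their inputs.

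**A NASH test read at different prevalences.**

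| p | Source | NPV | PPV |
|---|---|---|---|
| 4.5% | midpoint of population NASH, 4–5% | 99.1% | 7.8% |
| 25% | minimum NASH, 50 of 200 | 0.375/0.400 = 93.8% | 0.225/0.600 = 37.5% |
| 30% | population NAFLD | 0.350/0.380 = 92.1% | 0.270/0.620 = 43.5% |
| 50% | 50 NASH plus 50 NAFL of 200 | 0.250/0.300 = 83.3% | 0.450/0.700 = 64.3% |
| 80% | assumed enrolled NAFLD | 0.100/0.180 = 55.6% | 0.720/0.820 = 87.8% |

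The 50% row assumes that the second group in section 11.5 means NAFL, that both groups are at their minimum, and that nobody else has NAFLD. Even then, the same test is above 88% at its own prevalence (93.8% at 25%) and below it on the NAFLD axis (83.3%). Varying the assumed enrolled NAFLD prevalence from 75% to 90% moves NPV from 62.5% to 35.7%.

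**Intervals.** Take 50 NASH and 150 non-NASH at the same targets. At the sample prevalence there are counts: NPV 75/80 = 93.8%, exact interval 86.0 to 97.9%; PPV 45/120 = 37.5%, exact interval 28.8 to 46.8%. These are valid.

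At an assumed prevalence, NPV combines two independent proportions and there is no single count. The delta method on the logit scale gives variance se/[(1−se)n₁] + (1−sp)/(sp·n₀) = 9/50 + 1/150 = 0.187, standard error 0.432. At 30% the logit of NPV is ln(0.350/0.030) = 2.457, and the interval is 83.3 to 96.5%. At 80% it is ln(0.100/0.080) = 0.223, and the interval is 34.9 to 74.5%.

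**The case against.** The protocol uses NAFLD loosely. Section 11.5 lists NASH and NAFLD as if they were separate groups, and the objectives speak of histological findings of NAFLD in general. The synopsis may simply mean the prevalence of whichever finding is classified. That is fair as a guess at intent, and it is not established that anyone will compute a NASH NPV at NAFLD prevalence. But the wording does not say so, and substituting NAFL for NAFLD does not help, because a NASH test indexed by NAFL prevalence is also wrong.

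A curve over a range of prevalences can be read at any value, so a wrong label leaves its shape intact. This stands for the curve. It does not stand for the enrolled point, which has to be placed at one prevalence.

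The 30% and 4–5% figures describe the general population, not patients offered a biopsy. This also stands, so the contrast that matters is between NASH and NAFLD prevalence within the study.

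A reader might infer that the plan prescribes exact binomial intervals along the whole prevalence curve, and then that these would have wrong coverage. The documents do not support this. "with respective exact 95% confidence intervals" belongs to the sentence on point estimates, where observed counts exist. Exact binomial is named only for adverse event rates in section 11.7.4. Any coverage failure would depend on how pseudo-counts were built at other prevalences, which no section describes. The gap is an unspecified method, not a wrong one.

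**Conclusion.** The prevalence axis is wrong as written: it belongs to a condition that the cut-point does not classify. With 90% sensitivity and 50% specificity, NPV for NASH is 93.8% at the planned minimum of 25% NASH, 92.1% at 30%, and 55.6% at an assumed 80% enrolled NAFLD prevalence. The last figure rests on that assumption. The direction does not: where both NASH and NAFL are present, the NAFLD axis understates NPV and overstates PPV.

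The interval issue is smaller. Exact intervals are right for the observed table, and the plan is silent on intervals at assumed prevalences.

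The study is exploratory, its minimum criterion is an AUC of at least 0.75, and a separate study will validate the algorithm. None of those is affected. The point still deserves correction here, because predictive values support the rule-out claim and may shape the cut-off carried into validation.

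**What to change.** Amend the synopsis sentence and repeat it in section 11.7.5:

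- Plot PPV and NPV against the prevalence of the condition being classified, over a stated range: NASH prevalence for the NASH diagnosis and NAFL prevalence for the NAFL diagnosis.
- Mark the enrolled prevalence of that same condition on each plot.
- Keep exact intervals for sensitivity, specificity and the observed-sample PPV and NPV.
- At assumed prevalences, name a logit (delta-method) interval built from sensitivity and specificity, or a bootstrap. A bootstrap should repeat model fitting and cut-off selection if it is to reflect them.
- State the prevalence behind the 88% NPV target.

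This needs wording and standard code, and no change to patients, visits or sample size. The downside is that some intervals become wider. In the illustration at 80% prevalence, the logit interval of 34.9 to 74.5% compares with 38.1 to 72.1% if 200 subjects rescaled to that prevalence were treated as observed.
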